3.4 Study population

3.4.1 Patient population

The target population is comprised of adult patients with histologically-confirmed, advanced pancreatic neuroendocrine tumor. The study will enroll up to 44 patients. Patients must have

baseline evaluations performed prior to the first dose of study drug and must meet all inclusion and exclusion criteria. Results of all baseline evaluations, which assure that all inclusion and exclusion criteria have been satisfied, must be reviewed by the Principal Investigator or his/her designee prior to enrollment of that patient. In addition, the patient must be thoroughly informed about all aspects of the study, including the study visit schedule and required evaluations and all regulatory requirements for informed consent. The written informed consent must be obtained from the patient prior to enrollment. The following criteria apply to all patients enrolled onto the study unless otherwise specified.

Inclusion criteria

1. Locally unresectable or metastatic pancreatic neuroendocrine tumor.
 - Radiologic, operative, or pathology reports should document a pancreatic location of tumor.
 - Patients must have confirmed low-grade or intermediate-grade neuroendocrine carcinoma.
 - Patients with poorly differentiated neuroendocrine carcinoma, high-grade neuroendocrine carcinoma, adenocarcinoid, goblet cell carcinoid, and small cell carcinoma are not eligible.
2. Patients must have at least one measurable site of disease according to RECIST criteria that has not been previously irradiated. If the patient has had previous radiation, chemoembolization, or cryotherapy to the marker lesion(s), there must be evidence of progression since the radiation.
3. Age \geq 18 years.
4. Minimum of two weeks since any major surgery, completion of radiation, or completion of all prior systemic anticancer therapy (adequately recovered from the acute toxicities of any prior therapy).
5. Prior treatment with chemotherapy is allowed, with the exception of prior treatment with temozolomide or dacarbazine.
6. No prior therapy with RAD001 or any other mTOR inhibitor.
7. ECOG performance status \leq 2.
8. Life expectancy 12 weeks or more.
9. Adequate bone marrow function as shown by: ANC \geq $1.5 \times 10^9/L$, Platelets \geq $100 \times 10^9/L$, Hgb $>$ 9 g/dL.
10. Adequate liver function as shown by: serum bilirubin \leq 1.5 x upper limit of normal (ULN), and serum transaminases activity \leq 3 x ULN, with the exception of serum transaminases ($<$ 5 x ULN) if the patient has liver metastases.
11. Adequate renal function as shown by serum creatinine \leq 1.5 x ULN.
12. Fasting serum cholesterol \leq 300 mg/dL OR \leq 7.75 mmol/L AND fasting triglycerides \leq 2.5 x ULN. NOTE: In cases where one or both of these thresholds are exceeded, the patient can only be included after initiation of appropriate lipid lowering medication, see Section 4.4.6.

13. Women of childbearing potential must have a negative serum pregnancy test within 14 days of the administration of the first study treatment. Women must not be lactating. Both men and women of childbearing potential must be advised of the importance of using effective birth control measures during the course of the study.
14. Signed informed consent to participate in the study must be obtained from patients after they have been fully informed of the nature and potential risks by the investigator (or his/her designee) with the aid of written information.

Exclusion criteria

1. Prior treatment with any investigational drug within the preceding 4 weeks.
2. Chronic treatment with systemic steroids or another immunosuppressive agent, with the exception of patients receiving physiologic steroid replacement for adrenal insufficiency or other similar conditions.
3. Patients should not receive immunization with attenuated live vaccines during study period or within 1 week of study entry.
4. Uncontrolled brain or leptomeningeal metastases, including patients who continue to require glucocorticoids for brain or leptomeningeal metastases.
5. Other malignancies within the past 3 years except for adequately treated carcinoma of the cervix or basal or squamous cell carcinomas of the skin.
6. Patients who have any severe and/or uncontrolled medical conditions or other conditions that could affect their participation in the study such as:
 - Unstable angina pectoris, symptomatic congestive heart failure, myocardial infarction \leq 6 months prior to first study treatment, serious uncontrolled cardiac arrhythmia
 - Severely impaired lung function
 - Any active (acute or chronic) or uncontrolled infection/ disorders.
 - Nonmalignant medical illnesses that are uncontrolled or whose control may be jeopardized by the treatment with the study therapy
 - Liver disease such as cirrhosis, chronic active hepatitis or chronic persistent hepatitis
 - A known history of HIV seropositivity
 - Impairment of gastrointestinal function or gastrointestinal disease that may significantly alter the absorption of RAD001 (e.g., ulcerative disease, uncontrolled nausea, vomiting, diarrhea, malabsorption syndrome or small bowel resection)
7. Women who are pregnant or breast feeding, or women/men able to conceive and unwilling to practice an effective method of birth control. (Women of childbearing potential must have a negative serum pregnancy test within 14 days prior to administration of RAD001). Oral, implantable, or injectable contraceptives may be affected by cytochrome P450 interactions, and are therefore not considered effective for this study.
8. Patients who have received prior treatment with an mTOR inhibitor or temozolomide.
9. Patients with a known hypersensitivity to RAD001 (everolimus) or other rapamycins (sirolimus, temsirolimus) or to its excipients

10. History of noncompliance to medical regimens
11. Patients unwilling to or unable to comply with the protocol

4 Treatment Program

4.1 Study Treatment

The investigational study drugs used in the course of this trial are RAD001 and temozolomide:

- Cohort 1: Patients will receive an oral dose of 5 mg of RAD001 administered daily and an oral dose of temozolomide of 150 mg/m² daily for 7 days every other week beginning on Day 1 of RAD001 administration. Temozolomide will be administered for a maximum of 6 months; RAD001 may be administered until treatment progression, unacceptable or dose limiting toxicity, withdrawal of consent, or other reason for treatment discontinuation.
- Cohort 2: Patients will receive an oral dose of 10 mg of RAD001 administered daily and an oral dose of temozolomide of 150 mg/m² daily for 7 days every other week beginning on Day 1 of RAD001 administration. Temozolomide will be administered for a maximum of 6 months; RAD001 may be administered until treatment progression, unacceptable toxicity, withdrawal of consent, or other reason for treatment discontinuation.
- Cohort 3: Patients will receive an oral dose of RAD001 administered daily at the MTD as established in the phase I component of the study (Cohorts 1 and 2) and an oral dose of temozolomide of 150 mg/m² daily for 7 days every other week beginning on Day 1 of RAD001 administration. Temozolomide will be administered for a maximum of 6 months; RAD001 may be administered until treatment progression, unacceptable toxicity, withdrawal of consent, or other reason for treatment discontinuation.

Patients on study therapy may be at risk for temozolomide-related selective lymphopenia and opportunistic infections. To reduce the risk of opportunistic infections, patients will receive prophylaxis with Bactrim DS, 1 tablet by mouth every Monday, Wednesday, and Friday beginning after the first month of treatment. Patients allergic to Bactrim should be initiated on an alternate, standard PCP prophylaxis regimen. Previous infections associated with temozolomide-induced lymphopenia in neuroendocrine tumor patients have developed after more than 6 months of treatment. Treatment with temozolomide in this study will therefore be limited to a maximum duration of 6 months.

Novartis will supply RAD001, and Schering-Plough will provide temozolomide free of charge for study participants.

4.2 Interruption or discontinuation of treatment

For patients who are unable to tolerate the protocol-specified dosing schedule, dose adjustments are permitted in order to keep the patient on study drug. If administration of RAD001 or temozolomide must be interrupted because of unacceptable toxicity, drug dosing will be interrupted or modified according to rules described in Section 4.4. Toxicity will be assessed using the NIH-NCI Common Terminology Criteria for Adverse Events, version 3.0 (CTCAEv3.0, (<http://ctep.cancer.gov/forms/CTCAEv3.pdf>)).

All interruptions or changes to study drug administration must be recorded.

It will be documented whether or not each patient completed the clinical study. If for any patient either study treatment or observations were discontinued the reason will be recorded. Reasons that a patient may discontinue participation in a clinical study are considered to constitute one of the following:

1. adverse event(s)
2. abnormal laboratory value(s)
3. abnormal test procedure result(s)
4. disease progression
5. protocol violation
6. subject withdrew consent
7. lost to follow-up
8. administrative problems
9. death

4.3 Monitoring of suspected toxicities

Patients whose treatment is interrupted or permanently discontinued due to an adverse event or abnormal laboratory value suspected to be related to RAD001 or temozolomide must be followed at least weekly until the adverse event or abnormal laboratory resolves or returns to grade 1. If a patient requires a dose delay of > 21 days from the intended day of the next scheduled dose, then the patient must be discontinued from the study.

4.4 Dose Modification

4.4.1 RAD001 dose adjustments

Three RAD001 dose levels are defined for dose adjustment: 10 mg daily, 5 mg daily, and 5 mg every other day.

Table 4.1.1 : Dose Reduction Schedule for RAD001 – Cohort 1

Dose Level	Dose and schedule	Days per cycle (cycle length = 28 days)
0	5 mg daily	Continuous
Decrease 1 dose level	5 mg every other day	Continuous
Decrease 2 dose levels	Discontinue therapy	

Table 4.1.2 : Dose Reduction Schedule for RAD001 – Cohort 2

Dose Level	Dose and schedule	Days per cycle (cycle length = 28 days)
0	10 mg daily	Continuous
Decrease 1 dose level	5 mg daily	Continuous
Decrease 2 dose levels	5 mg every other day	Continuous
Decrease 3 dose levels	Discontinue therapy	

4.4.2 Temozolomide dose adjustments

Three temozolomide dose levels are defined for dose adjustment: 150 mg/m² daily, 100 mg/m² daily, and 50 mg/m² daily, administered on days 1-7 and days 15-21 of each cycle.

Table 4.2 : Dose Reduction Schedule for Temozolomide

Dose Level	Dose and schedule	Days per cycle (cycle length = 28 days)
0	150 mg/m ² daily	Days 1-7; 15-21
Decrease 1 dose level	100 mg/m ² daily	Days 1-7; 15-21
Decrease 2 dose levels	50 mg/m ² daily	Days 1-7; 15-21
Decrease 3 dose levels	Discontinue therapy	

4.4.3 Dose reductions for hematologic toxicity

Cohort 1: If the ANC is $<1,000$ or the platelet count is $<50,000$ during study therapy, RAD001 and temozolomide will be delayed. If RAD001 or temozolomide cannot be administered on the scheduled day of dosing, the CBC will be repeated weekly for up to and including 3 weeks until the ANC is $\geq 1000/\text{mm}^3$ and the platelet count $\geq 50,000/\text{mm}^3$. At that time, temozolomide will be reinitiated at one reduced dose level ($100 \text{ mg}/\text{m}^2$ daily, see Tables 4.1-4.2). The dose of RAD001 will remain at 5 mg daily. For subsequent dose reductions, both temozolomide and RAD001 will be reduced by one dose level. If treatment is held more than 3 weeks, the patient should be taken off protocol therapy.

Cohort 2: If the ANC is $<1,000$ or the platelet count is $<50,000$ during study therapy, RAD001 and temozolomide will be delayed. If RAD001 or temozolomide cannot be administered on the scheduled day of dosing, the CBC will be repeated weekly for up to and including 3 weeks until the ANC is $\geq 1000/\text{mm}^3$ and the platelet count $\geq 50,000/\text{mm}^3$. At that time, RAD001 and temozolomide will be reinitiated at one reduced dose level (see Tables 4.1-4.2). If treatment is held more than 3 weeks, the patient should be taken off protocol therapy.

Growth factors cannot be used to induce elevations in neutrophil count for the purposes of administration of RAD001 and temozolomide on the scheduled dosing OR to allow treatment. Administration of erythropoietin is allowed.

4.4.4 Dose reductions for non-hematologic toxicity

Both RAD001 and temozolomide should be held for all clinically significant drug related toxicities that are grade 3 or higher and not specified in the drug-specific toxicities below. All drug related CTCAE Grade 3 and 4 toxicities must have resolved to at least CTCAE Grade 1 prior to repeat dosing. For patients with baseline grade 2 elevations in transaminases or bilirubin or alkaline phosphatase, transaminase, bilirubin, or alkaline phosphatase levels must have resolved to the level defined by the Inclusion Criteria prior to repeat dosing.

Once toxicities have resolved to at least grade 1, RAD001 and temozolomide will be reinitiated at one reduced dose level per Table 4.3. If treatment is held more than 3 weeks, the patient should be taken off protocol therapy.

If multiple toxicities are seen, the dose administered should be based on the dose reduction required for the most severe grade of any single toxicity observed. If unacceptable toxicity occurs, therapy should be discontinued.

Table 4.3 Criteria for dose-modification of RAD001 and temozolomide for non-hematologic toxicity

Toxicity	Actions
Grade 2 (except pneumonitis [refer to Table 4.4] and mucositis)	If the toxicity is tolerable to the patient, maintain the same dose. If the toxicity is intolerable to patient, interrupt RAD001 and temozolomide until recovery to grade ≤ 1 . Then reintroduce RAD001 and temozolomide at one lower dose level.
Grade 2 mucositis	If the toxicity is tolerable to the patient, maintain the same dose. If the toxicity is intolerable to patient, interrupt RAD001 and temozolomide until recovery to grade ≤ 1 . Then reintroduce RAD001 at one lower dose level and continue same dose of temozolomide. See section 4.4.5 for further details.
Grade 3 (except hyperlipidemia and hyperglycemia and mucositis and pneumonitis)	Interrupt RAD001 and temozolomide until recovery to grade ≤ 1 . Then reintroduce both RAD001 and temozolomide at one lower dose level.
Grade 3 hyperlipidemia	Grade 3 hyperlipidemia (hypercholesterolemia and/or hypertriglyceridemia) should be managed using medical therapies, per section 4.4.6. Dose reduction of RAD001 or temozolomide can be considered but is not required.
Grade 3 hyperglycemia	Grade 3 hyperglycemia should be managed using medical therapies, per section 4.4.6. Dose reduction of RAD001 or temozolomide can be considered but is not required.
Grade 3 mucositis	For Grade 3 mucositis, interrupt RAD001 and temozolomide until recovery to grade ≤ 1 . Then reintroduce RAD001 at one lower dose level and continue temozolomide at same dose. See section 4.4.5 for further details.
Grade 3 pneumonitis	Please refer to Table 4.4.
Grade 4	Discontinue protocol therapy
Any non-hematological toxicity requiring interruption for > 3 weeks	Discontinue protocol therapy

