4.4.7 Management of non-infectious pneumonitis

Both asymptomatic radiological changes (grade 1) and symptomatic non-infectious pneumonitis (grade 2 = not interfering with activities of daily living or grade 3 = interfering with activities of daily living and oxygen indicated) have been noted in patients receiving RAD001 therapy. Non-infectious pneumonitis has been associated with RAD001 and other mTOR inhibitors (Atkins, 2004). In order to monitor for asymptomatic (grade 1) pulmonary infiltrates, a chest X-ray is required if a CT scan of chest is not used for bi-monthly disease evaluations. Additional chest X-rays/CT scans may be done, when clinically necessary. If non-infectious pneumonitis develops, consultation with a pulmonologist should be considered. Management of non-infectious pneumonitis suspected to be associated with RAD001 and dose modifications instructions are provided in Table 4.4.

Table 4.4 Management of non-infectious pneumonitis

Worst Grade Pneumonitis	Required Investigations	Management of Pneumonitis	Actions
Grade 1	CT scans with lung windows.	No specific therapy is required	Administer 100% of RAD001 and temozolomide doses.
Grade 2	CT scan with lung windows. Consider pulmonary function testing includes: spirometry, DLCO, and room air O ₂ saturation at rest. Repeat each subsequent Cycle until return to within normal limits. Consider a bronchoscopy.	Symptomatic only. Prescribe corticosteroids if cough is troublesome.	Discontinue study therapy until recovery to \leq grade 1. Study therapy may also be interrupted if symptoms are troublesome. If recovered, resume treatment with RAD001 and temozolomide at one lower dose level. Patients will be withdrawn from the study if they fail to recover to \leq grade 1 within 3 weeks.
Grade 3	CT scan with lung windows and pulmonary function testing includes: spirometry, DLCO, and room air O ₂ saturation at rest.; Repeat each subsequent Cycle until return to within normal limits. Bronchoscopy is	Prescribe corticosteroids if infective origin is ruled out. Taper as medically indicated.	Hold RAD001 and temozolomide until recovery to \leq grade 1. May restart RAD001 and temozolomide within 2 weeks at a reduced dose (by one level) if evidence of clinical benefit.

Worst Grade Pneumonitis	Required Investigations	Management of Pneumonitis	Actions
	recommended.		

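### Section 4.4.4 doses multiple non-hematologic toxicities by the highest grade, which can cancel a temozolomide reduction that a lower-grade event alone requires

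*Combined protocol and SAP*

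**What the plan says.** Section 4.4.4 covers non-hematologic toxicity. When there is more than one, "the dose administered should be based on the dose reduction required for the most severe grade of any single toxicity observed". The reductions themselves are in Table 4.3:

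- **Grade 3 mucositis.** Both drugs are interrupted until grade 1 or less. "Then reintroduce RAD001 at one lower dose level and continue temozolomide at same dose".
- **Grade 2, other than mucositis or pneumonitis, intolerable.** Both drugs are interrupted until grade 1 or less. "Then reintroduce RAD001 and temozolomide at one lower dose level".
- **Grade 2, tolerable.** "If the toxicity is tolerable to the patient, maintain the same dose". The point does not concern these patients.
- **Grade 3 hyperlipidemia or hyperglycemia.** Medical management; a reduction of either drug is optional.
- **Other Grade 3, except pneumonitis.** "Then reintroduce both RAD001 and temozolomide at one lower dose level".

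Pneumonitis is sent to Table 4.4, and Section 4.4.7 says that "dose modifications instructions are provided in Table 4.4". For Grade 2 pneumonitis that table reads: "If recovered, resume treatment with RAD001 and temozolomide at one lower dose level".

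Section 4.4.4 also has a general restart rule that lowers both drugs one level, but it defers to Table 4.3. Section 4.2 refers to the rules of Section 4.4, and Section 4.4.5 refers to Section 4.4.4 for the RAD001 dose in mucositis. None of these says what to do when two rows disagree about one drug.

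**The concern.** The rule selects one governing toxicity by grade and takes the dose of both drugs from it. It therefore assumes that required reductions rise with grade, drug by drug. The mucositis rows break that assumption because they spare temozolomide. The Grade 3 metabolic row breaks it because it requires no reduction of either drug.

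The result is an inversion: a patient with two toxicities can be assigned a higher restart dose than a patient with only the milder one. At stake is re-exposure, after recovery, at one dose level above what the plan requires for the milder event. Participating sites might also restart similar patients at different doses, depending on how literally they read the sentence.

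**Working it through.** The plan gives no figure to reproduce. The check applies the 4.4.4 sentence to Tables 4.2 and 4.3, for each toxicity alone and then together.

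**Levels by which each drug is lowered at restart**

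| Toxicity | RAD001 | Temozolomide |
|---|---|---|
| Grade 3 mucositis alone | 1 | 0 |
| Intolerable Grade 2 event alone (not mucositis or pneumonitis) | 1 | 1 |
| Both, highest grade governs (literal reading) | 1 | **0** |
| Both, largest reduction per drug | 1 | **1** |
| Grade 3 hyperlipidemia or hyperglycemia alone | 0 required | 0 required |
| Grade 3 metabolic plus intolerable Grade 2, literal reading | **0 required** | **0 required** |
| Grade 3 metabolic plus intolerable Grade 2, largest per drug | **1** | **1** |

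With mucositis, only temozolomide is affected. With a Grade 3 metabolic event both drugs are affected, but a reduction becomes optional rather than ruled out. Even within one metabolic toxicity the requirement can fall with grade: intolerable Grade 2 hyperglycemia comes under the general Grade 2 row (both drugs lower), while at Grade 3 nothing need be lowered.

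**Temozolomide dose gap.** Table 4.2 gives doses of 150, 100 and 50 mg/m² on days 1-7 and 15-21, then discontinuation. Dosing days per cycle = 7 + 7 = 14.

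| Level before the event | Literal reading, mg/m² per cycle | Required for the Grade 2 event alone | Difference |
|---|---|---|---|
| 150 mg/m² | 150 × 14 = 2,100 | 100 × 14 = 1,400 | 700 (ratio 1.5) |
| 100 mg/m² | 100 × 14 = 1,400 | 50 × 14 = 700 | 700 (ratio 2.0) |
| 50 mg/m² | 50 × 14 = 700 | discontinue | – |

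**RAD001 dose gap, metabolic case only.** Tables 4.1.1 and 4.1.2 cover Cohorts 1 and 2; I assume Cohort 3 follows the one that matches its starting dose. From 10 mg daily: 10 × 28 = 280 mg per cycle with no reduction, against 5 × 28 = 140 mg. From 5 mg daily: 140 mg, against 5 × 14 = 70 mg on alternate days. From 5 mg every other day, the next step is discontinuation.

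**Frequency.** The documents do not give the joint frequency. For scale only, Table 1-1 (RAD001 alone, drug-related events) shows stomatitis/mucositis of grade 3 or higher in 3 of 45 patients at 10 mg daily and 1 of 16 at 5 mg daily. If those rates carried over to the combination, which is an assumption, 32 × 3/45 = 2.1 or 32 × 1/16 = 2.0 of the 32 Cohort 3 patients would have such mucositis at all. Only those with a simultaneous intolerable Grade 2 event, while still on temozolomide, would meet the mucositis form of the problem.

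**The case against.** The strongest reply is that the sentence can be read sensibly. Grade 3 mucositis requires no temozolomide reduction, so the only temozolomide reduction required comes from the Grade 2 event, and the sentence merely forbids adding reductions. Section 4.4.5 links mucositis to RAD001, so keeping temozolomide unchanged naturally means that mucositis is no reason to cut it, not that it cancels another reason. This is a fair account of what was probably intended, and many investigators would act on it. It nevertheless replaces the most severe grade with the largest reduction, which the text does not say. The general restart rule does not help, because it defers to the table that holds the mucositis exception.

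The stakes are also small, and that stands. Both drugs are held until grade 1 or less for Grade 3 mucositis and for the intolerable Grade 2 event. A hold over 3 weeks ends protocol therapy, and "If unacceptable toxicity occurs, therapy should be discontinued". If the Grade 2 event later recurs alone and is again intolerable, its own row lowers temozolomide. Myelosuppression, which the appended temozolomide label calls dose-limiting, is handled separately in Section 4.4.3.

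A reader might extend the point to Grade 2 pneumonitis with Grade 3 mucositis. The documents do not support this well: Table 4.3 excludes pneumonitis from its Grade 2 row, and Section 4.4.7 places its dosing in Table 4.4, which lowers both drugs. Table 4.4 probably prevails.

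A reader might also accumulate the gap: with six temozolomide cycles and the event in the first, 5 × 700 = 3,500 mg/m². That is not a measure of harm. It describes a patient who recovered and then needed no further reduction for five cycles.

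**Conclusion.** The point holds as a defect of wording with a safety direction. Taken literally, the multiple-toxicity sentence restarts temozolomide one level too high (700 mg/m² more per cycle from 150 or 100 mg/m²; continuation rather than discontinuation from 50 mg/m²) when Grade 3 mucositis accompanies an intolerable Grade 2 event other than mucositis or pneumonitis. It also removes the mandatory reduction of both drugs when the higher-grade event is Grade 3 hyperlipidemia or hyperglycemia.

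This rests on reading the most severe grade as the deciding criterion, on the Grade 2 event being intolerable, and on no other section resolving the conflict. A reader might infer that patients are dosed through unresolved toxicity, or that the response rate, error rates or sample size are affected. The documents support neither: the issue arises only at restart, and nothing in Section 10 depends on it. Severity is low, and the case for acting is that the repair is cheap.

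**What to change.** Replace the multiple-toxicity sentence in Section 4.4.4 with:

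*Where more than one toxicity is present, apply to each drug separately the largest single dose reduction (or discontinuation) required by any one of them under Tables 4.3 and 4.4; reductions are not added together.*

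This also settles a related ambiguity: mucositis alongside another toxicity of the same grade that lowers both drugs, where the present sentence does not say which temozolomide instruction applies. Discretion for a Grade 3 metabolic event on its own, and the conditional restart after Grade 3 pneumonitis, are unchanged. Combinations with hematologic toxicity (Section 4.4.3) are outside this fix.

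The cost is an amendment with the reviews that Section 8 requires (Novartis, the investigator and the IRB); Appendix B, Section 5.4 may class it as major because it changes treatment. It needs no extra patients, visits or tests. The downside is that the few affected patients receive one level less temozolomide, and also one level less RAD001 when the higher-grade event is Grade 3 hyperlipidemia or hyperglycemia. A patient already at the lowest level of a drug reaches the discontinuation step, as the Grade 2 event alone would already require.
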